2.1 CLINICAL STUDIES PERFORMED WITH THE LIGHT ADJUSTABLE LENS AND LIGHT DELIVERY DEVICE

US Phase III Study Conducted Under IDE G100240

A 600 eye prospective, randomized, controlled, multi-center clinical trial of the LAL and LDD designed to evaluate safety and effectiveness over a 12-month period was conducted at 17 sites. In addition to the visual correction of aphakia, reduction in residual spherocylindrical refractive error and improvement in uncorrected visual acuity were evaluated following LAL implantation and subsequent refractive adjustment of the LAL by the LDD.

Eyes with ≥ 0.75 and ≤ 2.5 diopters (D) of keratometric cylinder were randomly assigned to receive either the LAL or a commercially available, posterior chamber, non-accommodating, control monofocal IOL. Six hundred eyes were implanted with 403 eyes randomized to the LAL group and 197 eyes to the Control group.

Co-primary effectiveness endpoints included percent reduction in manifest cylinder, percent mean absolute reduction in manifest refraction spherical equivalent (MRSE), and rotation of the LAL. All primary effectiveness endpoints compared pre-adjustment (LAL) or 17-21 days (Control) to 6 months postoperatively and the first two endpoints compared results between the LAL and Control groups. All three co-primary effectiveness endpoints were met with a p-value <0.0001 . The difference in means for percent reduction in manifest cylinder was 54.7%, with a p-value <0.0001 . The difference in means for percent reduction in absolute MRSE was 41.1% with a p-value <0.0001 . Rotation of the LAL of ≤ 5 degrees was observed in 96.1% of LAL implanted eyes with both the upper and lower bound of the 95% confidence interval exceeding the requirement of 90%.

100% of eyes in both the LAL and Control groups had BSCVA of 20/40 or better, exceeding the historic grid rate of 92.5% (ISO 11979-7). The incidence of sight-threatening complications and adverse events for the LAL and Control groups were also below the threshold rates calculated from the 1-year historical grid for intraocular lenses (ISO 11979-7, Ophthalmic implants- Intraocular lenses- Part 7: Clinical investigations) except for the category of Secondary Surgical Interventions (SSI), which was significantly higher than the historical rate ($p<.05$).

On November 22, 2017, the Center for Devices and Radiological Health (CDRH) of the Food and Drug Administration (FDA) approved RxSight's premarket approval application (PMA) for the Light Adjustable Lens (LAL) and Light Delivery Device (LDD) system. This system is indicated for the reduction of residual astigmatism to improve uncorrected visual acuity after removal of the cataractous natural lens by phacoemulsification and implantation of the intraocular lens in the capsular bag; in adult patients:

- With pre-existing corneal astigmatism of ≥ 0.75 diopters
- Without pre-existing macular disease

The system also reduces the likelihood of clinically significant residual spherical refractive errors.

⁸ Hengerer FH, Bocker J, Dick BH, Conrad-Hengerer I. Light adjustable lens. New options for customized correction of presbyopia. Ophthalmologe. 2012 Jul; 109(7): 676-82.

3 STUDY OBJECTIVE

The objective of this study is to evaluate, for the visual correction of aphakia, whether the RxSight Light Adjustable Lens (LAL) and Light Delivery Device (LDD) can be used to improve visual outcomes after performing adjustments of the LAL with the LDD. This is an exploratory study. No primary effectiveness endpoints will be identified.

4 STUDY DESIGN

A prospective, controlled, single center, exploratory clinical study will be conducted. Subjects will be followed until the completion of a Postop Month 3 or later visit. Subjects who were enrolled under protocol version 05 will be reconsented prior to undergoing a Postop Month 3 or later visit. Subjects who were enrolled under protocol version 05 and exited from the study after their Postop Months 1-2 visit will be reconsented prior to undergoing the Postop Month 3 or later visit.

Patients who require cataract extraction and intraocular lens implantation will be screened for eligibility. If one or both eyes meet inclusion/exclusion criteria, study staff will explain the study purpose, procedures, risks/benefits and subject responsibilities to the potential participant. Written informed consent will be obtained prior to any study specific testing. The patient is enrolled upon signing the informed consent. If both eyes of the subject are enrolled for study participation, each eye will be scheduled for surgery within a timeframe of the investigator's choice but on separate days.

Commencing at the Postop Week 3 visit, all eyes will receive two to three adjustments and one to two lock-in treatments. Each light treatment will be separated by 3 to 7 days. [REDACTED]

[REDACTED]

[REDACTED]

Postoperatively, all subjects will undergo complete ophthalmic examinations at regular intervals.

For subjects that receive only spherical/sphero-cylindrical adjustments, distance visual acuities will be presented and summarized. For subjects that receive a presbyopia adjustment, distance, intermediate, and near visual acuities and depth of focus (DOF) curves will be presented and summarized. Additional analyses may be performed. Safety for all study eyes will be evaluated per ISO 11979-7.

DURATION OF STUDY

Each subject will participate in the study for 3-9 months. Time of participation is dependent on the date of the Postop Month 3 or later visit. [REDACTED]

[REDACTED]

STUDY SITE

The study will be performed in an ophthalmology clinic. The investigator will be an ophthalmic surgeon, specializing in cataract surgery with implantation of intraocular lenses.

Study responsibilities will be registered in a delegation log that will be kept at the investigational site. The overall responsibility at the study clinic remains with the investigator.

5 OUTCOME PARAMETERS

The following visual performance parameters will be collected and summarized for subjects that received only spherical/sphero-cylindrical adjustments.

- % of eyes with UCDVA of 20/20 or better at Postop Month 1-2 and the Postop Month 3 or later visit.

The following visual performance parameters will be collected and summarized for subjects that were bilaterally implanted with the LAL and received a presbyopia adjustment.

- Proportion of subjects simultaneously with (1) Binocular UCDVA of 20/20 or better and (2) Binocular UCIVA of 20/25 or better and (3) Binocular UCNVA of 20/40 or better at Postop Month 1-2 and the Postop Month 3 or later visit.
- Change in pseudoaccommodation (D) at Postop Month 1-2 and the Postop Month 3 or later visit from pre-light adjustment at Postop Week 3

Additional analyses may be performed. Clinical data for subjects receiving only spherical/sphero-cylindrical adjustments and subjects receiving a presbyopia adjustment will be summarized and analyzed separately.

SAFETY PARAMETERS

- Incidence of cumulative ocular serious adverse events defined per ISO 11979-7.

The incidence of all other adverse events will also be presented.

6 STUDY POPULATION

The study population will consist of up to 200 eyes in up to 200 subjects (one or two eyes per subject).

Both eyes of all subjects should be screened for eligibility. If at any time during the screening, an eye does not meet inclusion or exclusion criteria, screening for that eye will be discontinued.

6.1 REQUIRED INCLUSION CRITERIA

- Must sign a written Informed Consent form and be willing to undergo cataract surgery for unilateral or bilateral implantation of the LAL.
- Between the ages of 40 and 80 inclusive on the day the cataract surgery is performed.
- Study eye must have preoperative keratometric cylinder ≤ 3.50 D.
- Study eye must have a cataract causing reduction in best corrected distance visual acuity (BCDVA) to a level of 20/32 or worse with or without a glare source.
- Study eye must have BCDVA projected (by clinical estimate based upon past ocular history or retinal exam) to be 20/20 or better after cataract removal and IOL implantation.
- If only one eye of a subject is enrolled, the non-study eye must have the potential for BCVDA of 20/40 or better.
- Study eye has clear intraocular media other than cataract.
- Willing and able to comply with the requirements for study specific procedures and visits.
- Study eye has a dilated pupil diameter of ≥ 7.0 mm.
- Study eye has an undilated distance viewing pupil diameter > 2.5 mm.
- Study eye requires an IOL power within the range available for the LAL.

6.2 OPTIONAL INCLUSION CRITERIA

- Study eye was previously enrolled within clinical study CSP-026 sponsored by RxSight, Inc.

6.3 REQUIRED EXCLUSION CRITERIA

- Serious co-morbid conditions that in the judgment of the investigator makes inclusion in the study not in the best interest of the subject.
- Study eye with pseudoexfoliation.
- Study eye with diabetes with any evidence of retinopathy.
- Study eye with evidence of glaucomatous optic neuropathy.
- Study eye with history of uveitis.
- Study eye with significant anterior segment pathology, such as rubeosis iridis, aniridia, or iris coloboma.

- Study eye with corneal pathology or corneal dystrophy that is either progressive or sufficient to reduce BCDVA to worse than 20/20.
- Study eye with clinically significant dry eye syndrome (DES).
- Study eye with keratoconus or suspected of having keratoconus.
- Study eye with prior history of Intacs, Radial keratotomy (RK), Conductive keratoplasty (CK), Astigmatic keratotomy (AK), Phakic Implantable Collamer Lens (ICL), Corneal Inlay, intraocular surgery, or with previous pterygium excision unless the pterygium did not extend more than 2mm onto the cornea from the limbus.
- Subjects taking systemic medication that may increase sensitivity to UV light such as tetracycline, doxycycline, psoralens, amiodarone, phenothiazines, chloroquine, hydrochlorothiazide, hypericin, ketoprofen, piroxicam, lomefloxacin, and methoxsalen. LDD treatment in patients taking such medications may lead to irreversible phototoxic damage to the eye. This is only a partial list of photosensitizing medications. Please evaluate all medications that the patient is taking for this effect prior to consideration for implantation.
- Subjects taking a systemic medication that is considered toxic to the retina such as tamoxifen.
- Study eye with irregular astigmatism.
- Study eye with a history of ocular herpes simplex virus.
- Subjects who the doctor believes will be unable to maintain steady fixation that is necessary for centration of the LDD light treatment.
- Study eye with previous trauma or developmental defects in which appropriate support of the intraocular lens (IOL) is not possible.
- Study eye with current vitreoretinal disease or are at a high risk for future vitreoretinal disease that may require silicone oil as part of therapy.

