7.2 SUBJECT ENTRY

Patients who require cataract extraction and intraocular lens implantation will have both eyes screened for eligibility. If one or both eyes meet inclusion/exclusion criteria, study staff will explain the study purpose, procedures, risk/benefits and subject responsibilities to the potential participant. Written informed consent will be obtained prior to any study specific testing. The patient is enrolled upon signing the informed consent. The subject will sign and date the informed consent form in the presence of the person conducting the consent process. The investigator and/or the person conducting the consent process will also sign and date the consent form. During the study, the subject will be provided with any new information that is received that could affect their health status or change their willingness to continue to participate in the study. The preoperative examination will be performed no more than 60 days prior to surgery. If the 60-day time period elapses, it is acceptable for patients to be re-screened by undergoing a complete preoperative examination. Ocular dominance testing will be performed as part of the preoperative evaluation to determine eye dominance. If both eyes of the subject are enrolled for study participation, each eye will be scheduled for surgery within a timeframe of the investigator's choice but on separate days.

Only subjects meeting all inclusion/exclusion criteria will be implanted. Those subjects who do not meet the inclusion/exclusion requirements will be considered screen failures. Unique identification numbers will be assigned to each subject.

The implant lens power for the LAL will be calculated based upon the ocular biometry data and a lens power formula of the surgeon's choice. A postoperative spherical equivalent (SE) outcome of the physician's choice will be targeted.

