7.3.2 LIGHT TREATMENT PROCEDURE

Seventeen (17) to 24 days after surgery, the subject will return for the Postop Week 3 evaluation and a 1st adjustment treatment of the LAL. Subsequent second and third adjustment treatments, if necessary, will all be separated by 3-7 days. The subject will receive the 1st lock-in treatment 3-7 days after the final adjustment treatment. If necessary, lock-in #2 may be performed 3-7 days after lock-in #1. Depending on the adjustment(s) performed, all eyes will receive two to three adjustments and one or two lock-in treatments.

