7.3.2.1 Postponement of Light Treatment Procedure(s)

LDD treatment should be delayed if any of the following new symptoms or changes in performance are noted;

- Best Corrected Distance Visual Acuity: With any loss of BCDVA (unless the cause is known to be non-retinal) of 10 letters or more on an ETDRS (logMAR) chart compared to the Postop Week 3 BCDVA, treatment should be delayed.

- If sutures were utilized at the time of surgery to close the incision wound, light treatments should not commence on the study eye until a minimum of 4 weeks after suture removal.⁹
- A study eye with an ocular adverse event that could be negatively impacted by light treatment or negatively impact the effectiveness or safety of a light treatment should have light treatments delayed until after the adverse event has subsided. This includes corneal edema and superficial punctate keratitis (SPK) (Grade 3 (moderate) or more severe), retinal conditions including diabetic retinopathy and cystoid macular edema, epithelial defect, and endophthalmitis.
- If a study eye is discovered with evidence of premature photopolymerization as evidenced as a zone on the lens surface, the investigator should contact the Sponsor for further instructions. (see [REDACTED] for additional details regarding premature photopolymerization).
- Any study eye possessing clinically significant posterior capsular (PC) haze should undergo a YAG capsulotomy procedure prior to the adjustment. A minimum of 48 hours should separate the YAG treatment from the corresponding refraction and LDD adjustment.

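### The protocol warns of irreversible damage if LDD light is given to a subject on a photosensitizing drug, but no readable rule requires a re-check or hold when such a drug is started after implantation

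*Combined protocol and SAP*

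**What the plan says.** Section 6.3 (repeated in the synopsis) excludes subjects taking systemic drugs that raise sensitivity to UV light, gives a list that it calls partial, and warns: "LDD treatment in patients taking such medications may lead to irreversible phototoxic damage to the eye". It then sets the time of the drug evaluation: "Please evaluate all medications that the patient is taking for this effect prior to consideration for implantation". Section 7.2 applies the criteria at the same point: "Only subjects meeting all inclusion/exclusion criteria will be implanted".

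Light comes later. Section 7.3.2 says "Seventeen (17) to 24 days after surgery, the subject will return for the Postop Week 3 evaluation" and the first adjustment, and that "all eyes will receive two to three adjustments and one or two lock-in treatments". The same section describes the second and third adjustments as given if necessary, and Section 7.4 marks Adjustment #2 as if needed.

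Section 7.3.2.1 governs postponement: "LDD treatment should be delayed if any of the following new symptoms or changes in performance are noted". Its five bullets cover loss of BCDVA, sutures, an ocular adverse event, premature photopolymerization and posterior capsular haze. The adverse-event bullet names "retinal conditions including diabetic retinopathy and cystoid macular edema" among its examples.

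Table 1 in Section 7.5 has a row for ocular history including medications, marked at all ten scheduled visits. These include the five at which light may be given.

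**The concern.** Section 6.3 makes drug use at the time of UV exposure the danger, but the control it states acts earlier, at the decision to implant. A subject who passes that check and is then prescribed, say, doxycycline or hydrochlorothiazide (both on the Section 6.3 list) is no longer covered by a stated rule. Eligibility has already been applied. Section 7.7.4 does not allow withdrawal after implantation unless the lens is explanted. Section 7.3.2 has every eye go on to light treatment.

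At stake is harm to an individual eye. Section 6.3 calls the possible damage irreversible, and Section 10.6 says UV damage to the cornea and retina may be permanent. Only drug use that overlaps a light treatment carries this risk.

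**Working it through.** The plan gives no figure on this point to reproduce. The check has two parts: how long after the stated drug evaluation light is given, and whether any readable text acts on a drug started in that interval.

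**Timing, for eyes with no postponement.** Inputs from Sections 7.3.2 and 7.4: first adjustment on Day 17 to 24; each later light treatment 3 to 7 days after the one before; at most three adjustments and two lock-ins.

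| Case | Treatments | Final lock-in | First to last light |
|---|---|---|---|
| Latest: 3 adjustments, 2 lock-ins | 3 + 2 = 5 | 24 + 7 + 7 + 7 + 7 = Day 52 | 4 × 7 = 28 days |
| Earliest, two adjustments mandatory, 1 lock-in | 2 + 1 = 3 | 17 + 3 + 3 = Day 23 | 3 + 3 = 6 days |
| Earliest, second adjustment optional, 1 lock-in | 1 + 1 = 2 | 17 + 3 = Day 20 | 3 days |

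The two lower bounds reflect two statements in the protocol that do not agree: all eyes receive two to three adjustments, and the second adjustment is given only if needed. On either reading, every light treatment falls at least 17 days and, in window, at most 52 days after implantation, the point at which eligibility is applied.

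**Does any readable text act on a drug started after implantation?**

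- *Section 7.3.2.1.* BCDVA loss, sutures, premature photopolymerization and capsular haze are not drug exposures. The adverse-event bullet needs an event in the eye. For phototoxic injury, that bullet and the BCDVA bullet would act only once there was something to find, whereas the Section 6.3 hazard comes from taking the drug. The bullets themselves are readable; the only redaction among them is a cross-reference about photopolymerization.
- *Sections 7.3.2.3 to 7.3.2.5.* The readable preparation, adjustment and lock-in steps cover dilation, positioning, data entry, alignment, aborted treatments and eyewear. None mentions systemic medication. Adjustment step 10 is redacted.
- *Table 1.* The medication row is marked at all five light visits, so a new drug may come to notice on the day of light. No readable text says what to do then. The row is labelled as ocular history, and the readable text does not say that it captures systemic drugs.

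The readable plan therefore states the hazard and a check before implantation, but neither a re-check nor an action afterwards. The number of subjects who would start such a drug cannot be derived from the documents, and no rate is assumed.

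**The case against.** The strongest reply is that the warning is already about light. Section 6.3 names the treatment, the hazard and example drugs, and the investigator is an ophthalmic surgeon with a general duty under Section 10.4.1 to protect the subject. Someone who learned of a new photosensitizing drug would probably hold treatment. This stands, and it limits the point: what is missing is an explicit instruction, not knowledge of the hazard. But Section 7.3.2.1 writes out holds that a surgeon could also infer, such as those for sutures and corneal edema, and inferring a hold depends on first asking about new drugs.

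Second, a rule may exist elsewhere. The LDD Operator's manual is not available here, parts of the light-treatment text are redacted, and the consent pages were removed. This also stands. A reader might infer that the study ran without any such rule; the documents do not show that.

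Other stronger readings are tempting and should be resisted:

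- *The protocol directs light in a subject on such a drug.* It does not. The hold list does not say it is exhaustive, and the Section 6.3 warning points the other way.
- *Drugs were singled out for omission, because the exclusion "Study eye with diabetes with any evidence of retinopathy" reappears in the hold list.* Diabetic retinopathy appears there only as an example of an ocular adverse event. Other Section 6.3 exclusions, such as uveitis and ocular herpes simplex, are not named there either, so the list was not built by re-applying Section 6.3.
- *The same gap applies to retina-toxic drugs such as tamoxifen.* Section 6.3 excludes these, but attaches the warning about LDD light only to photosensitizing drugs.

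Section 7.1.1 also describes a UV-filtering posterior layer that limits retinal exposure. It is a mitigation, though it does not protect the cornea, and the Section 6.3 warning is given for this lens.

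**Conclusion.** The concern holds for the readable plan. The stated drug evaluation precedes implantation, light follows from Day 17 to at most Day 52 in window with up to 5 UV treatments per eye, and no readable rule requires a re-check or hold for a photosensitizing drug started in between. The lower bound is 3 treatments ending on Day 23 or 2 ending on Day 20, depending on whether the second adjustment is mandatory. These figures describe the period of possible exposure; they do not measure risk.

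The point is a modest but worthwhile patient-safety improvement. A reader might infer that the safety or effectiveness results are compromised, but the documents give no support for that: the analyses are descriptive, and no planned estimate depends on this rule. The conclusion assumes that neither the unseen manual nor the redacted text already contains a hold. If one does, a cross-reference in Section 7.3.2.1 would be enough.

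**What to change.** Add one bullet to Section 7.3.2.1, along these lines:

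*Before each adjustment and lock-in, ask about systemic medications started since implantation. If a photosensitizing medication (see Section 6.3) is in use, delay the light treatment and contact the Sponsor for instructions on stopping or substituting the drug and on when to resume. UV spectacle wear continues until 24 hours after the final lock-in.*

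Contacting the Sponsor follows the pattern already used in that section for premature photopolymerization, and the spectacle rule repeats Section 7.3.2.4. The question fits visits at which a medication entry is already scheduled, but it should name systemic drugs expressly.

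The real cost falls on the subjects held. Their lens stays unlocked and they wear UV spectacles for longer, and Section 10.6 notes that UV exposure before lock-in can change vision unpredictably. With a long-term drug the delay could become open-ended. The Sponsor and investigator should therefore document a release decision that weighs phototoxic risk against leaving the lens unlocked. The documents give no basis for a fixed deadline: the 3 to 7 days between light treatments is a spacing rule and was not set for this purpose.
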